4. OBJECTIVES

The registry is aimed at developing a high-quality set of data regarding the percutaneous localization of PPNs. The localization registry itself is nested within the subjects' lung resection operation. Analyzing and promulgating evidence-based best practices for lung nodule localization will allow surgeons to identify technical solutions and reproducible methods.

This registry will record procedural data for trained thoracic surgeons using the SPiN Thoracic Navigation System™ and tools. Diagnostic yield will measure successful localization of the lesion in the resected specimen. Localization-related safety events will be collected.

4.1 Primary Objective:

Successful percutaneous localization of PPN.

To evaluate the accuracy of percutaneous nodule localization using the SPiN Thoracic Navigation System™ and its accessories, Veran will record the percentage of successful resections that result in the complete removal of the patient's nodule, with a negative margin. The diagnostic yield is calculated as the percentage of patients who have intra-operative localizations resulting in complete removal of nodule, divided by the total number of evaluable subjects. Evaluable subjects are those who complete the localization procedure.

Primary Objective: Successful percutaneous localization of PPN.

This is defined as the percentage of subjects in whom the nodule is successfully localized and removed in the first resected specimen. A pathological specimen with clear margins will count as a successful localization.

4.2 Safety Objective:

Collect safety data for localization procedure.

4.3 Secondary Objectives:

Secondary Objectives: Use as per synopsis – including margin.

- 4.3.1 Report localization methods and techniques – dye and materials used, volume of dye (methylene blue, ICG etc.), other materials such as microcoils, hook wires etc. Details regarding these techniques will be collected.
- 4.3.2 Collect data on intraoperative percutaneous localization time and duration of total surgical procedure.
- 4.3.3 Record nodule characteristics, including location in the lobe, distance from pleura, distance from surface of skin to target, morphological appearance, solid vs. ground glass etc.
- 4.3.4 Record weight of excised tissue and margin.
- 4.3.5 Report type of surgical resection performed (segmentectomy or wedge) and resection technique (VATS, RATS, thoracotomy).

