Localization of the peripheral nodules in the outer lung regions can be accomplished intraoperatively, just prior to surgical resection, with the same surgical staff who are performing the operation. This eliminates an additional step for the thoracic surgeon (or other oncology team member) and also for the subject, namely identifying and coordinating with persons from other departments who may typically place fiducial, hookwire, and microcoils as separate procedures, involving additional resources. In addition, the migration of these markers, and the need to verify their placement with an additional CT or other scan prior to surgery, are potentially steps that may be able to be streamlined. The overarching objective is to keep this localization and resection procedure within the hands of the principal investigator, and to quantify the percentage of subjects in whom the nodule is removed in the first resected specimen, procedure time, and nodule characteristics and procedure details and techniques.

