9.2 Primary Efficacy Objective: Successful Percutaneous Localization of PPN

This is defined as the percentage of subjects in whom the nodule is successfully localized and removed in the first resected specimen. A pathological specimen with clear margins will count as a successful localization.

To evaluate the accuracy of percutaneous nodule localization using the SPiN Thoracic Navigation System™ and its accessories, by recording the percentage of successful nodule resections that result in the complete removal of the patient's nodule, with at least a one cell perimeter and negative margins. The diagnostic yield is calculated as the percentage of patients who have intra-operative localizations resulting in complete removal of nodule, divided by the total number of evaluable subjects.

Confirmation of Diagnosis

Surgical pathology results will determine the outcome of the primary endpoint. If the patient has follow-up imaging that shows a decrease in size or resolution of the nodule, the nodule will be determined to be of benign etiology if the study pathology yields a benign diagnosis (granuloma, inflammation, fibrosis, infection). To verify final diagnosis, a copy of the final pathology report will be de-identified and provided by the site. The pathology findings will then identify the case as either benign or malignant. Whether a benign or malignant diagnosis is made, the primary endpoint is met.

If Margins are Intact

If the nodule has intact margins as described by the pathology report. Explicitly, a perimeter of at least one cell around the nodule contain cells that are all non-malignant. This plus the nodule sample verifies that the entire nodule was removed. The pathology findings will then identify the case as either benign or malignant.

Crossover Cases

It is anticipated that there will be cases where the wedge is positive for malignancy and the deep margin also will be positive. In these cases, the surgical plan may change from a planned wedgeectomy into a completion lobectomy or segmentectomy. If the nodule is fully removed

(having at least a cell's margin of non-malignant cells in these cases, then the primary endpoint is met. The pathology findings will then identify the entire case as either benign or malignant, and the primary endpoint is met.

Margins for Crossover Cases

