If the nodule is fully removed in crossover cases, then the primary endpoint is met. The nodule may be removed per the surgeon's judgement. The pathology findings will then identify the entire case as either benign or malignant, and the primary endpoint is met.

If Diagnosis is Non-malignant

If the nodule is deemed non-malignant, cells are identifiable, then the positive box for diagnosis is checked, and:

- The nodule must have an intact margin of a cell as a perimeter to be diagnostic.
- The type of nodule (ground glass opacity, etc.) is collected from the pathology report.

The pathology findings will then identify the case as either benign or malignant.

9.3 Safety Objective:

Record Safety Events During Intraoperative Percutaneous Localization Only

To collect and evaluate the safety of nodule localization, including incidence and severity of localization-procedure related adverse events (AEs) and serious adverse events (SAEs) that occur during the localization procedure.

Baseline/Enrollment

All patients will be provided with information about the registry and will sign the informed consent form before any registry-related assessments are made. The following data will be collected at baseline for all enrolled patients:

- To be collected at baseline visit: Review of inclusion/exclusion criteria.

Localization Period

- The localization period begins when the needle touches the subject's skin.
- Localization ends when the localization needle is withdrawn from the subject for the final time.
- Any adverse events that develop during the localization procedure will be reported.
- Bronchoscopy-related events that occur during the alignment of the CT with the patient ("registration") will be recorded.
- Percutaneous localization step, injection of dye, injection of any microcoils, etc.

The process used for AE reporting conforms to Veran Medical Technologies, Inc., standard operating procedures (SOPs) for Medical Device Reporting (MDR)(Appendix C). Training on AE/SAE/MDR reporting practices will be provided to each participating site.

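### Crossover cases cleared only by a completion resection count as primary successes, although the primary rate is defined on the first resected specimen

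*Combined protocol and SAP*

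**What the plan says.** **Primary definition.** The synopsis (Primary Objective), Section 4.1 and Section 9.2 all define success as the nodule being localized and removed in the first resected specimen, with clear margins counting as successful localization. Section 2 gives the same aim: "to quantify the percentage of subjects in whom the nodule is removed in the first resected specimen".

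**Crossover rule.** Section 9.2, under Crossover Cases, expects some malignant wedges to have a positive deep margin, after which "the surgical plan may change from a planned wedgeectomy into a completion lobectomy or segmentectomy". Under Margins for Crossover Cases it then states: "If the nodule is fully removed in crossover cases, then the primary endpoint is met".

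**Label.** Section 4.1 introduces the measure with "To evaluate the accuracy of percutaneous nodule localization" and says that "Veran will record the percentage of successful resections that result in the complete removal" of the nodule with a negative margin. Section 9.2 repeats the accuracy aim and adds "with at least a one cell perimeter and negative margins". The denominator is all evaluable subjects, whatever resection follows. The synopsis (Study Procedures) leaves the choice of resection to the investigator.

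**Related outputs.** The secondary objectives in Section 4.3 include "Report type of surgical resection performed (segmentectomy or wedge) and resection technique" and "Record weight of excised tissue and margin". Section 9 (Crossover to Other Procedures) collects both the planned and the eventual surgery. The synopsis (Statistical Analysis) permits summaries by treatment subgroup without requiring them, and Section 11.2.1 leaves the analyses to a written SAP.

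**The concern.** A subject whose wedge has a positive deep margin has not had the nodule completely removed in the first specimen. If a completion lobectomy or segmentectomy then clears it, the crossover text turns that subject into a success. What changed the result was the extent of surgery, not the mark. Two analysts working from Section 9.2 could report different primary rates from the same data, and each could cite the protocol.

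This matters because the registry tests no hypothesis. The labelled estimate with its interval is the main product, and it is meant to inform best practice in localization. A reader of the headline figure would take it to describe first specimens.

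The label raises a related question. Complete removal with a negative margin reflects both where the mark was placed and how much tissue was taken. Presented as accuracy and pooled over resection types, it may be read as a direct measure of the mark, which it is not.

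**Working it through.** The plan states no expected rate, no number of crossovers and no mix of resections, so there is no figure of its own to reproduce. The only inputs taken from it are the size, 70 to 100 evaluable subjects, and the 95% confidence level (both Section 11.1). Everything else below is assumed.

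**1. One subject under the two rules.** Planned wedge, positive deep margin, completion resection clears the nodule.

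| Text | Specimen judged | Score |
|---|---|---|
| Synopsis, Section 4.1, opening of Section 9.2 | first | not a success |
| Section 9.2, crossover paragraphs | first plus completion | success |

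The rules cannot both hold for this subject.

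**2. Effect of crediting crossovers.** If k cases are credited among n subjects, the rate rises by k/n.

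- One case: 1/70 = 1.4 points; 1/100 = 1.0 point.
- Three cases: 3/70 = 4.3 points; 3/100 = 3.0 points.
- Five cases: 5/70 = 7.1 points; 5/100 = 5.0 points.

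With exact (Clopper-Pearson) 95% intervals and assumed counts:

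- First specimens only: 56/70 = 80.0% (68.7 to 88.6).
- Three of the 14 failures credited: 59/70 = 84.3% (73.6 to 91.9).

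The shift is a scoring choice and not sampling error, so the interval would not reveal it.

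**3. Effect of pooling over types of first resection.** Let f be the share of first resections larger than a wedge, w the success rate after wedge and a the rate after a larger resection. Then pooled rate minus wedge rate = f × (a − w).

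| Assumed w and a | f = 5% | f = 10% | f = 20% |
|---|---|---|---|
| w 75–85%, a 95–99% | 0.5 to 1.2 | 1.0 to 2.4 | 2.0 to 4.8 |
| w 90%, a 98% | 0.4 | 0.8 | 1.6 |
| w = a | 0 | 0 | 0 |
| w 90%, a 85% (harder nodules get larger resections) | −0.25 | −0.5 | −1.0 |

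Entries are percentage points. For example, 20% × (99% − 75%) = 4.8. If f = 0 the difference is zero.

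**4. The opposite direction.** On first-specimen scoring, a correctly marked nodule with a positive margin is a failure. Each such case lowers the rate by 1/n, again 1.4 points at 70 and 1.0 at 100. As a measure of accuracy the rate can therefore err either way.

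**5. Precision of a split.** At f = 10% to 20% the larger-resection group has 7 to 14 of 70 subjects, or 10 to 20 of 100. Exact 95% intervals run from 59.0 to 100% at 7/7 and from 83.2 to 100% at 20/20. In the wedge group at f = 20% of 70, 45/56 = 80.4% has the interval 67.6 to 89.8, little wider than that for 56/70.

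**The case against.** **The crossover paragraphs may be a deliberate exception.** Section 9.2 could be read as a general rule with a stated carve-out. It does not present itself that way, and neither the synopsis nor Section 4.1 mentions an exception. A rate reported under the first-specimen definition would then contain subjects who do not meet it. The conflict stands.

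**Crediting crossovers may come closer to accuracy.** A positive deep margin need not mean that the mark was misplaced, so scoring the case as a failure can be unfair to the mark. That is true, and it is why the rate should not be called accuracy. But the credit depends on whether the completion resection cleared the nodule, not on where the mark lay, so it does not correct the problem it might seem to address.

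**Wedge is the usual next step.** Sections 9 (Adverse Events), 9.9, 10 and 10.3 all describe a wedge following localization, and the synopsis restricts the population to subjects in whom the surgeon judged localization to be warranted. A reader might infer that larger first resections inflate the pooled rate. The documents do not establish this. They give no resection mix, and the share may be zero. That a larger first resection depends less on the mark is an inference: the crossover text concerns completion after a wedge, not a planned segmentectomy.

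**The split may already be intended.** A reader might infer that no breakdown by resection type will be made. The text does not support that either, because subgroup summaries are allowed and the analyses are deferred to a SAP. What can be said is that the supplied text does not commit to one.

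**The registry is descriptive and the pooled rate answers its aim.** Agreed. The pooled first-specimen rate should stay. The change concerns its scoring, its name and one companion table.

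**Conclusion.** The contradiction in scoring is plain in the text and should be corrected. Its effect is exactly 1/n per credited case, 1.4 points at 70 subjects and 1.0 at 100. The total depends on a number of crossovers that the documents do not give. The move from 80.0% to 84.3% illustrates three cases and is not a forecast.

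The labelling point is secondary. Complete removal with a negative margin is a proxy for localization accuracy that can err in either direction. Under the assumed inputs, pooling over first-resection type shifts the rate by between −1.0 and 4.8 points, and by nothing if every first resection is a wedge. The stronger conclusion, that the reported rate will overstate accuracy, is not supported.

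**What to change.** 1. **One scoring rule.** Amend the two crossover paragraphs of Section 9.2 so that the primary rate is scored on the first resected specimen, as the synopsis and Section 4.1 already say. Report subjects cleared by a completion resection on a separate line.
2. **Name.** In Sections 4.1 and 9.2, describe the rate as complete resection in the first specimen after localization, and drop the claim that it measures accuracy.
3. **One table.** Commit in the SAP to first-specimen success with exact 95% intervals by planned first resection (wedge versus larger), marked as descriptive. The planned and eventual surgery are already collected. Confirm that the eCRF records the resection type of the first specimen, because the eventual surgery may be the completion procedure.

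The cost is wording, one table and possibly one eCRF field. No subjects, visits or changes to care are added. The headline rate may be slightly lower than with crossovers credited, and the interval for the larger-resection group will be too wide to support more than description.

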9.3 Subject Enrolment and Informed Consent

Patients presenting to their physician in need of assessment or removal of peripheral pulmonary nodule(s), and who meet study inclusion/exclusion criteria, will be invited to participate. Patient enrolment will follow each participating institution's standard of care. Subjects will be approached to obtain informed consent prior to any study-specific procedure. Informed consent will take place in a private environment (e.g. patient exam room), free from distractions. The PI or study team member will approach the subject at their clinic appointment and will explain the study to qualified subjects prior to obtaining consent. All individuals who obtain consent (PI, Sub-investigators, and study coordinators) must have received GCP informed consent training within the past 2 years. Interviews to obtain consent will not follow any stressful situation (e.g. patient being informed he/she may have cancer) and will not be conducted if the patient has received any mind-altering medications or anesthesia. Patients will be assessed for their capacity to consent by the ability to show comprehension of the procedure, ask appropriate questions, and appear properly oriented.

The PI will confirm subject eligibility. Patients who sign the informed consent form will be considered enrolled. A signed copy of all consents and the HIPAA authorization document will also be given to consenting subjects.

Patients who complete the localization procedure will be included within the analysis population. Reasons for study withdrawal will be recorded. Each patient's participation in this study is approximately 6 weeks baseline through subject's discharge from hospital following lung surgery.

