9.4 Withdrawal of Subjects

Following informed consent, subjects withdrawn from the study prior to the localization procedure due to patient withdrawal of consent or at the discretion of the investigator will be considered withdrawn. In the case of investigator withdrawal, the reason for early withdrawal will be documented. Data collected from all treated patients undergoing localization will be included within the analysis population.

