11. STATISTICAL METHODS

11.1 Sample Size

This is an observational study where no formal hypothesis is being tested, data collected during the study will be summarized using descriptive statistics. No formal sample size estimations were utilized to determine the size of the study population. Generally, demographic and other descriptive characteristics of the cohorts will be described as counts and percentages for categorical variables and as measures of central tendency (mean, median, standard deviation [SD], and range) for continuous variables. Ninety-five percent (95%) confidence intervals will be computed for measures of effect and association. In some cases, data may be summarized by demographic.

The study will have 70-100 evaluable patients from approximately 5 sites in the US who undergo percutaneous localization followed by surgical resection. Evaluable patients are those who undergo the percutaneous nodule localization procedure and meet the inclusion/exclusion criteria. Each site will be expected to enroll a minimum of 6 subjects at their site.

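### The denominator of the primary localization rate, evaluable subjects, is defined in two different ways, and the plan does not say whether or how an abandoned localization counts

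*Combined protocol and SAP*

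**What the plan says.** Sections 4.1 and 9.2 both express the primary result as complete removals "divided by the total number of evaluable subjects". Section 9.2 does not define the term. Two other sections do, differently:

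- Section 4.1: "Evaluable subjects are those who complete the localization procedure".
- Section 11.1: "Evaluable patients are those who undergo the percutaneous nodule localization procedure and meet the inclusion/exclusion criteria".

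The wording for the analysis population varies in the same way:

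- Section 9.3 (Subject Enrolment and Informed Consent): "Patients who complete the localization procedure will be included within the analysis population".
- Section 9.4: "Data collected from all treated patients undergoing localization will be included within the analysis population".
- The Study Population row of the synopsis describes subjects who undergo dye or wire localization and then resection.

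No section defines completion for the denominator. The Localization Period text in section 9.3 (Safety Objective) runs from needle contact with the skin to the last needle withdrawal. It does not mention evaluable subjects, and it does not require that the nodule was reached or marked.

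For scoring, sections 4.1 and 9.2 count subjects in whom "the nodule is successfully localized and removed in the first resected specimen". The next sentence reads: "A pathological specimen with clear margins will count as a successful localization". Section 11.2.2 promises only the proportion of missing data for each variable.

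**The concern.** The endpoint is meant to show how accurately the system localizes nodules. Section 3 acknowledges that these nodules can be hard to find and reach for marking, so some localizations may foreseeably be started and then given up. Those cases say most about the limits of the technique. A denominator restricted to completers could remove them without the reader seeing it.

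The two definitions differ in two respects: completing versus undergoing the procedure, and whether eligibility is required. There is also a scoring gap. Suppose the surgeon gives up on marking, finds the nodule by other means and resects it with clear margins. The first sentence of the endpoint definition points to failure, because the nodule was not successfully localized. The second points to success, because the margins are clear. Two analysts could therefore report different primary rates from the same data, each with support in the text.

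**Working it through.** **Is there a planned figure to reproduce?** No. Section 11.1 plans 70-100 evaluable patients and states that no formal sample size estimation was made. No success rate, abandonment rate or target precision is given, and the interval method is not named. All inputs below are therefore assumptions, and intervals are exact (Clopper-Pearson) 95%.

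**Formula.** Let *p* be the success rate among completers, *a* the share of started localizations that are abandoned, and *q* the share of abandoned cases scored as successes. The rate among all started is (1 - *a*)*p* + *aq*, so

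completer rate minus all-started rate = *a*(*p* - *q*).

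The gap is positive when abandoned cases succeed less often than completers. It is zero when *q* = *p* and negative when *q* > *p*.

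**Abandoned cases all scored as failures (*q* = 0), 100 started:**

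| Abandoned | Completers only | All started | Gap (points) |
|---|---|---|---|
| 2 | 88/98 = 89.8% | 88/100 = 88.0% | 1.8 |
| 5 | 86/95 = 90.5% | 86/100 = 86.0% | 4.5 |
| 10 | 81/90 = 90.0% | 81/100 = 81.0% | 9.0 |

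At 10 abandoned, the intervals are 81.9-95.3% for completers and 71.9-88.2% for all started.

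**10 of 100 abandoned, some scored as successes on clear margins.** The completer rate stays at 90.0%.

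| Abandoned cases scored as success | All started (95% CI) | Gap (points) |
|---|---|---|
| 0 of 10 | 81.0% (71.9-88.2) | +9.0 |
| 5 of 10 | 86.0% (77.6-92.1) | +4.0 |
| 9 of 10 | 90.0% (82.4-95.1) | 0.0 |
| 10 of 10 | 91.0% (83.6-95.8) | -1.0 |

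**Lower end of the planned size: 70 started, 2 abandoned.** Completers 61/68 = 89.7%. All started is 61/70 = 87.1% with both as failures (gap 2.6 points), or 63/70 = 90.0% with both as successes.

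**Eligibility condition in section 11.1.** Start from 81/100 = 81.0% and suppose that 2 of the 100 are found ineligible after the procedure. If both were successes, the rate becomes 79/98 = 80.6%, a change of -0.4 points. If both were failures, it becomes 81/98 = 82.7%, a change of +1.7 points.

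**The case against.** The strongest reply is that the conflict may be only verbal. If a subject completes localization at the last needle withdrawal, as the Localization Period text could suggest, everyone with needle contact is in under either wording. Sections 9.3 (Subject Enrolment) and 9.4 can also be read together, since neither says that only those patients are included. A reader might infer that the plan openly excludes failed localizations, or that these two sections contradict each other. The documents support neither inference. The conflict lies between sections 4.1 and 11.1, and the exclusion follows only if completion means that the nodule was marked. Even so, the last-withdrawal text serves safety collection and is not tied to the denominator, and adopting it would still leave the eligibility mismatch and the scoring gap.

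It is also fair to say that the registry is descriptive, that the sizes are assumed, and that section 11.2.1 defers analysis detail to a written SAP. With 2 of 70 abandoned, the 2.6-point gap is small beside the exact interval of 77.0-93.9% for 61/70. These points limit the weight of the concern. They do not remove it: with no hypothesis test, the percentage and its interval are the main result. Section 11.2.1 also calls for summaries at least bi-annually, and a SAP built on this text would inherit both definitions.

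The eligibility objection largely stands. The investigator confirms eligibility, and subjects found ineligible before the procedure are screen failures under section 9.5, so few cases should remain.

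**Conclusion.** The concern holds as a conflict in a stated rule. The primary denominator has two definitions, completion is undefined, and the scoring of an abandoned localization is unsettled. On the ordinary reading of section 4.1, abandoned cases drop out, and the rate rises if they are technique failures.

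A reader might infer that the reported rate will be inflated by some definite amount. The documents do not support that. They give no success or abandonment rate, and even the direction depends on scoring. At 10% abandonment with 90% completer success, the gap runs from +9.0 points to -1.0; with no abandonment it is zero. The eligibility mismatch is worth about -0.4 to +1.7 points in the example.

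No test or sample-size calculation is affected. The mismatch in the text is certain; its numerical consequence is not. It should be fixed before the rate is next summarized.

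**What to change.** Use one definition in the synopsis (Study Population), sections 4.1, 9.2, 9.3 (Subject Enrolment), 9.4 and 11.1, and the SAP:

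- **Denominator.** Every consented subject in whom localization was started, taking needle contact with the skin, already in section 9.3 (Safety Objective), as the start. Judge any eligibility condition on pre-procedure data only.
- **Scoring.** Define completion. Count a started but abandoned localization as not successfully localized. Amend the clear-margin sentence in sections 4.1 and 9.2 so that it applies only where the nodule was localized; otherwise the two rules collide.
- **Sensitivity analyses, labelled as such.** (1) The completer-only rate. (2) The all-started rate with clear-margin abandoned cases counted as successes.
- **Registration.** Section 9.9 places registration before needle contact, so subjects stopped there fall outside this denominator although they too may be technique failures. Report their number, with a sensitivity rate that counts them as failures.

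The cost is small: no new patients or procedures. The headline rate may be slightly less favourable. The database must record the stage and reason for non-completion if it does not already. Section 9.9 lists registration among the data collected, and Table 1 and section 9.3 (Subject Enrolment) provide for reasons for discontinuation or withdrawal, but the full list of data elements is not visible here.
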